The primary efficacy endpoint of HI-E per IWG (Cheson, 2006) is defined as proportion of subjects meeting HI-E criteria of ≥ 1.5 g/dL increase in Hgb sustained over any consecutive 56-day period in the absence of RBC transfusions from W1D1 through Week 24. Subjects discontinued from the treatment period without achieving HI-E will be counted as non-responders. Dose modification guidance for luspatercept in Section 7.2.2 defines that, if predose Hgb is ≥ 12.0 g/dL at the day of dosing, the dose should be delayed until Hgb is < 11.0 g/dL. For subjects who meet this criterion and then have their dose delayed, if their Hgb levels temporarily decrease to < 1.5 g/dL but achieve ≥ 1.5 g/dL again after treatment resumption, this period (ie, the time from dose delay to achieving a Hgb increase of ≥ 1.5 g/dL again) will be included as the period of sustained Hgb increase of ≥ 1.5 g/dL.

As the primary efficacy analysis, one sample binomial one sided exact test will be performed based on intent-to-treat (ITT) population, to provide p-value (significance level: 0.025). The number and percentage of subjects who achieve the response and 95% confidence interval (CI) will be presented based on the ITT population.

There is no planned interim analysis for this study.

The primary analysis will be performed when all enrolled subjects have completed 24 weeks of treatment or discontinued before 24 weeks.

Additional follow-up analysis for efficacy and safety will be performed when all subjects have been followed for 5 years from the date of the first dose of IP, or 3 years from the last dose (whichever occurs later) during the Post-Treatment Follow-Up Period of the study.

For more details on statistical considerations please refer to Section 9 of the protocol.

TABLE OF CONTENTS

TITLE PAGE	1
PROTOCOL SUMMARY	6
TABLE OF CONTENTS	12
LIST OF TABLES	18
LIST OF FIGURES	19
1. INTRODUCTION	20
1.1. Myelodysplastic Syndromes	20
1.1.1. Current Treatment Options for Lower Risk MDS.....	21
1.1.1.1. Erythropoiesis Stimulating Agents.....	21
1.1.1.2. Red Blood Cell Transfusions	22
1.1.1.3. Lenalidomide.....	23
1.1.1.4. Hypomethylating Agents	23
1.2. Luspatercept Background	23
1.2.1. Mechanism of Action	23
1.2.2. Nonclinical Studies with Luspatercept	25
1.2.3. Summary of Clinical Experience	25
1.2.3.1. Potential Risks of Human Use	26
1.2.3.2. Overall Benefit Risk Assessment	27
1.3. Rationale	27
1.3.1. Study Rationale and Purpose	27
1.3.2. Rationale for the Study Design	28

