	Hematologic improvement in erythroid response (HI-E) per IWG (Cheson, 2006)	Proportion of subjects achieving HI-E over any consecutive 56-day period in the absence of RBC transfusions	W1D1 through Week 48
	Time to HI-E	Time from first dose to first onset of achieving ≥ 1.5 g/dL increase in hemoglobin over any consecutive 56-day period in the absence of RBC transfusions	W1D1 through Week 24; W1D1 through Week 48
	Time to mHI-E	Time from first dose to first onset of achieving ≥ 1.5 g/dL mean increase in Hgb compared to baseline over any consecutive 56-day period in the absence of RBC transfusions	W1D1 through Week 24; W1D1 through Week 48
	Duration of HI-E	Maximum duration of achieving ≥ 1.5 g/dL increase in hemoglobin for subjects who achieve Hgb increase ≥ 56 days in the absence of RBC transfusions	W1D1 through EOT
	Duration of mHI-E	Maximum duration of achieving ≥ 1.5 g/dL mean increase in Hgb compared to baseline for subjects who achieve mean Hgb increase ≥ 56 days in the absence of RBC transfusions	W1D1 through EOT
	RBC-TI	Proportion of subjects who maintain RBC-TI from W1D1 through Week 24, 48, and 72.	W1D1 through Week 24; W1D1 through Week 48; W1D1 through Week 72
	Safety	Type, frequency, severity of AEs and relationship of AEs to luspatercept	Screening through 42 days post last dose
	PK	C_{\max} , AUC, T_{\max}	W1D1 through 1-year post first dose

Table 2: Study Endpoints (Continued)

Endpoint	Name	Description	Timeframe
Secondary	Antidrug antibodies (ADA)	Frequency of antidrug antibodies and effects on efficacy, or safety, or PK	W1D1 through 1-year post first dose
	Progression to AML	Number and percentage of subjects progressing to AML; time to AML progression	W1D1 through 5 years from first dose or 3 years from last dose (whichever occurs later)
	Overall survival	Time from date of W1D1 to death due to any cause	W1D1 through 5 years from first dose or 3 years from last dose (whichever occurs later)
Exploratory	Molecular and cellular markers in the bone marrow and/or in peripheral blood	Evaluation of biomarkers that may potentially impact luspatercept efficacy, predict response or relapse, help to better understand MOA and/or provide further prognostic classification of MDS subtypes. Molecular markers (eg, SF3B1) include evaluation of MDS-associated gene mutations and their impact on drug efficacy, clinical response or relapse, disease progression, drug MOA and prognostication of MDS.	Baseline through End of Treatment

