4.2. Inclusion Criteria

Subjects must satisfy the following criteria to be enrolled in the study:

1. Subject is \geq 20 years of age the time of signing the informed consent form (ICF)
2. Subject must understand and voluntarily sign an ICF prior to any study-related assessments/procedures being conducted.
3. Subject is willing and able to adhere to the study visit schedule and other protocol requirements.
4. Subject has a documented diagnosis of MDS according to WHO 2016 classification (Section 6.1.1, Appendix B) that meets IPSS-R classification (Greenberg, 2012) of very low, low, or intermediate risk disease, and:
 - < 5% blasts in bone marrow
5. Subject has symptomatic anemia with mean Hgb concentration < 10.0 g/dL from 2 measurements (one performed within 1 day prior to W1D1 and the other performed 7 to 35 days prior to W1D1) that does not require RBC transfusion. If more than one measurement exists in the period of 7 to 35 days prior to W1D1, the most recent value will be used.
6. Subject must be TI, as documented by the following criteria:
 - No RBC transfusion administered within 16 weeks prior to W1D1 (except transfusions due to blood loss or infection that occurred between 16 and 8 weeks prior to W1D1)
7. Subject has Eastern Cooperative Oncology Group (ECOG) score of 0, 1, or 2
8. Females of childbearing potential (FCBP), defined as a sexually mature woman who: 1) has achieved menarche at some point, 2) not undergone a hysterectomy or bilateral oophorectomy, or 3) has not been naturally postmenopausal (amenorrhea following cancer therapy or amenorrhea due to other medical reasons does not rule out childbearing potential) for at least 24 consecutive months (ie, has had menses at any time in the preceding 24 consecutive months), must:
 - Have two negative pregnancy tests as verified by the investigator prior to starting study therapy (unless the screening pregnancy test was done within 72 hours of W1D1). Refer to Section 6.1.14 for additional details. She must agree to ongoing pregnancy testing during the course of the study, and after end of study treatment. This applies even if the subject practices true abstinence¹ from heterosexual contact.

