6.3.2. Long-term Follow-up

Transfusion data collection will continue until 8 weeks from the date of last dose of IP or from the date of the EOT Visit (whichever is later) (Section 6.4.1). Subjects should also be followed via telephone contact by the site to verify if transfusions were given outside of the investigative site.

Antidrug antibodies sample(s) may be required in the Post-Treatment Follow-up Period for subjects who terminate the Treatment Period with less than 1 year of ADA monitoring if a subject is ADA positive at the time of treatment discontinuation (Section 6.6).

All subjects discontinued from protocol-prescribed therapy for any reason should be followed for the below events/therapies for 5 years from the date of the first dose of IP, or 3 years from the last dose (whichever occurs later), or until death, lost to follow-up or withdrawal of consent from the study.

- Progression to AML and other malignancies/pre-malignancies (please refer to Section 6.1.20 and Section 10.5 for details)
- Survival (date and cause of death)
- and subsequent MDS therapies

Subjects may be followed via telephone contact by the site for collection of the above data every 12 weeks for the first 3 years from the date of last dose of IP and every 6 months thereafter (if applicable) until 5 years from the date of the first dose of IP, or 3 years from the last dose (whichever occurs later), or until death, lost to follow-up or withdrawal of consent from the study. Refer to Table 3.

Data regarding subsequent MDS therapies, determination of AML progression and other malignancies/pre-malignancies, and date and cause of death will be recorded in the eCRF. The investigator must make every effort to obtain information regarding the subject's survival status before determining the subject is lost to follow-up. If the subject is discontinued from Long-term Follow-up, the reason for discontinuation should be recorded on the End of Study eCRF.

Long-term follow-up may be conducted by record review (including public records if allowed by local regulations) and/or telephone contact with the subject, family, or the subject's treating physician.

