9.6.2. Secondary Efficacy Analyses

The secondary variables will be analyzed descriptively, unless otherwise specified, and will be based on the ITT population and EE population. Kaplan-Meier methods will be used to estimate curves for time to event secondary variables. Counts and percentages will be used to describe categorical variables. Response rate of HI-E per IWG ([Cheson, 2006](#)) within 24 weeks, based on the EE population, will be analyzed as a secondary endpoint.

Modified hematologic improvement - erythroid (mHI-E) per IWG ([Cheson, 2006](#)) is defined as proportion of subjects meeting mHI-E criteria of ≥ 1.5 g/dL mean increase in Hgb compared to baseline that is sustained over any consecutive 56-day period in the absence of RBC

transfusions from W1D1 through Week 24 (and W1D1 through Week 48) of the Treatment Period. Subjects discontinued from the Treatment Period without achieving a mean Hgb increase ≥ 1.5 g/dL will be counted as non-responders.

HI-E per IWG (Cheson, 2006) within 48 weeks is defined as proportion of subjects meeting HI-E criteria of ≥ 1.5 g/dL increase in Hgb sustained over any consecutive 56-day period in the absence of RBC transfusions from W1D1 through Week 48 of the Treatment Period. Subjects discontinued from the Treatment Period without achieving HI-E will be counted as non-responders.

For subjects who have a dose delay meeting the dose modification criterion described in Section 9.6.1, if their Hgb levels temporarily decrease to < 1.5 g/dL but achieve ≥ 1.5 g/dL again after treatment resumption, this period (ie, the time from dose delay to achieving a Hgb increase of ≥ 1.5 g/dL again) will be included as the period of sustained Hgb increase of ≥ 1.5 g/dL.

Time to HI-E will be summarized only for subjects who achieve HI-E. It is defined as time from W1D1 to first onset of achieving ≥ 1.5 g/dL increase in Hgb over any consecutive 56-day period in the absence of RBC transfusions. It will be summarized separately for subjects who achieve HI-E within the first 24 weeks and 48 weeks from W1D1, respectively.

Time to mHI-E will be summarized only for subjects who achieve mHI-E. It is defined as the time from W1D1 to first onset of achieving ≥ 1.5 g/dL mean increase in Hgb over any consecutive 56-day period in the absence of RBC transfusions. It will be summarized separately for subjects who achieve mHI-E within the first 24 weeks and 48 weeks from W1D1, respectively.

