Duration of HI-E will be determined only for subjects who achieve HI-E during the Treatment Period. Duration of HI-E is defined as the maximum duration of achieving ≥ 1.5 g/dL increase in Hgb for subjects who achieve Hgb increase ≥ 56 days in the absence of RBC transfusions. Subjects who maintain HI-E through the end of the Treatment Period or time of analysis will be censored at the date of treatment discontinuation/time of analysis or death, whichever occurs first.

Duration of mHI-E will be determined only for subjects who achieve mHI-E during the Treatment Period. Duration of mHI-E is defined as the maximum duration of achieving ≥ 1.5 g/dL mean increase in Hgb for subjects who achieve a mean Hgb increase of ≥ 56 days in the absence of RBC transfusions. Subjects who maintain mHI-E through the end of the Treatment Period or time of analysis will be censored at the date of treatment discontinuation/time of analysis or death, whichever occurs first.

Proportion of subjects who maintain RBC-TI is defined as proportion of subjects not being given any RBC transfusion during the Treatment Period and will be calculated at Week 24, Week 48, and Week 72.

Time to progression to AML is defined as the time between W1D1 and first diagnosis of AML as per WHO classification of $\geq 20\%$ blasts in peripheral blood or bone marrow. Subjects with diagnosis of AML will be considered to have had an event. Subjects who have not progressed to AML at the time of analysis will be censored at the last assessment date which does not indicate progression to AML.

Overall survival (OS) is defined as the time between W1D1 and death/censored date. Subjects who die, regardless of the cause of death, will be considered to have had an event. Subjects who are alive at the time of analysis will be censored at the last assessment date at which the subject was known to be alive. All subjects who were lost to follow-up will also be censored at the time of last contact.

Full analysis details will be included in the SAP.

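### Section 9.6.2 censors deaths without AML in the Kaplan-Meier analysis of time to AML, so one minus that curve overstates the probability of AML, by roughly 2 to 6 points at 5 years under stated assumptions

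*Combined protocol and SAP*

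**What the plan says.** Table 2 (section 2) lists the AML endpoint as "Number and percentage of subjects progressing to AML; time to AML progression", followed to 5 years from first dose or 3 years from last dose, whichever is later.

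Section 9.6.2 supplies the method in three parts:

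- Estimator: "Kaplan-Meier methods will be used to estimate curves for time to event secondary variables".
- Event: "Subjects with diagnosis of AML will be considered to have had an event".
- Censoring: "Subjects who have not progressed to AML at the time of analysis will be censored at the last assessment date", that date being the last assessment without evidence of AML.

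The AML rule does not mention death. The rules for duration of HI-E and mHI-E in the same section do: subjects still in response "will be censored at the date of treatment discontinuation/time of analysis or death, whichever occurs first". The overall survival rule also deals with death explicitly. Section 9.6.2 closes by leaving full details to the SAP. The documents supplied contain no separate SAP text on time to AML and name no competing-risk method.

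The curve matters mainly at the last analysis. The Protocol Summary says: "Additional follow-up analysis for efficacy and safety will be performed when all subjects have been followed for 5 years" from first dose, or 3 years from last dose if that is later.

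**The concern.** A subject who dies without AML has not progressed, so the only rule that covers this subject is the censoring rule. Kaplan-Meier treats a censored subject as having the same future risk of AML as those still under observation. That is wrong for someone who has died. Their weight passes to the survivors, and one minus the curve estimates AML risk in a setting where nobody dies first, which is not the risk these patients face.

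Such deaths are to be expected. Section 1.1 says that about half of lower-risk patients die of something other than MDS or AML. Appendix C gives median survival of 5.3 years (Low) and 3.0 years (Intermediate), against follow-up of at least 5 years.

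At stake is the consistency of one safety-relevant endpoint. With complete follow-up, the planned percentage progressing equals the cumulative incidence. The complement of the Kaplan-Meier curve, from the same subjects, is higher whenever an AML-free death precedes an AML event. The report could then carry two AML figures that disagree, with the higher one biased.

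**Working it through.** The plan states no AML probability to reproduce. Its one design figure, 95% power for HI-E with 20 subjects, is not in dispute: rejecting at 6 or more responders gives an exact alpha of 0.0113 and power of 94.5%.

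**Inputs (Appendix C, years)**

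| | Very Low | Low | Intermediate |
|---|---|---|---|
| Median survival | 8.8 | 5.3 | 3.0 |
| Time to 25% AML | not reached | 10.8 | 3.2 |
| Share of cohort | 19% | 38% | 20% |

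**Assumptions**

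- Hazards are constant.
- The 25% AML times are cause-specific quantities. The documents do not say how deaths were handled there.
- AML-free death occurs at a fraction f of the all-cause hazard. I use f = 0.5 and f = 1; the latter is an upper bound.
- The case mix is assumed, because the protocol gives no expected IPSS-R distribution.

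**Hazards per year**

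- AML: a = -ln(0.75)/t25. Low 0.2877/10.8 = 0.0266; Intermediate 0.2877/3.2 = 0.0899.
- AML-free death: d = f × ln2/median survival. At f = 1: Very Low 0.0788, Low 0.1308, Intermediate 0.2310.

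**Within one risk category at 5 years**

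- Deaths censored: 1 − KM = 1 − exp(−5a).
- Death as competing event: CIF = a/(a+d) × (1 − exp(−5(a+d))).

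| | 1 − KM | CIF, f = 0.5 | CIF, f = 1 | Gap (points) |
|---|---|---|---|---|
| Low | 12.5% | 10.7% | 9.2% | 1.8 to 3.3 |
| Intermediate | 36.2% | 28.1% | 22.4% | 8.1 to 13.8 |

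**Pooled cohort**, two-thirds Low and one-third Intermediate. With weights w and S(t) = exp(−(a+d)t) in each category, the pooled 1 − KM is 1 − exp(−∫ Σ(w·a·S)/Σ(w·S) dt), and the CIF is the weighted sum of the category CIFs. Gaps are taken before rounding.

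| Year | f = 0.5: 1 − KM vs CIF | Gap | f = 1: 1 − KM vs CIF | Gap |
|---|---|---|---|---|
| 1 | 4.59% vs 4.41% | 0.18 | 4.55% vs 4.21% | 0.35 |
| 3 | 12.7% vs 11.4% | 1.4 | 12.5% vs 10.0% | 2.5 |
| 5 | 19.8% vs 16.5% | 3.3 | 19.2% vs 13.6% | 5.6 |

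**Sensitivity at 5 years**

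- Mix 19:38:20 including Very Low, whose AML hazard is varied from zero to the Low value: gap 2.1 to 2.6 (f = 0.5) and 3.5 to 4.5 (f = 1).
- Two-thirds/one-third mix with the Intermediate AML hazard halved, because section 4.2 requires "< 5% blasts in bone marrow": 14.8% vs 12.3% and 14.6% vs 10.2%, a gap of 2.5 to 4.4.
- Both risks low (5 to 10% AML and 20% AML-free death by 5 years, each taken alone): gap about 0.5 to 1.
- Appendix C's 25% AML times read instead as cumulative incidences: gap 2.5 to 6.0 for Low and 9.3 to 17.9 for Intermediate.

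**What one trial of 20 would show.** I simulated 40,000 trials of 13 Low and 7 Intermediate subjects with complete 5-year follow-up.

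| | f = 0.5 | f = 1 |
|---|---|---|
| Mean AML events | 3.3 | 2.8 |
| Mean AML-free deaths | 5.9 | 9.9 |
| Mean 1 − KM | 20.0% | 19.5% |
| SD of 1 − KM (points) | 9.7 | 10.8 |
| Mean percentage progressing | 16.7% | 13.9% |
| 1 − KM exceeds percentage by more than 5 points | 21% of trials | 47% of trials |
| 1 − KM exceeds percentage by more than 10 points | 2.5% of trials | 15% of trials |

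A hand example with the least favourable ordering: 6 of 20 die without AML, and then 3 of the remaining 14 progress. The percentage is 3/20 = 15.0%. One minus Kaplan-Meier is 1 − (13/14)(12/13)(11/12) = 3/14 = 21.4%.

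**The case against.** The strongest reply has four parts.

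- **The plan promises a curve and does not commit to reading its complement as AML risk.** Censoring deaths is valid for the cause-specific hazard, and the absolute risk is already covered by the planned percentage. This is fair as far as it goes. But section 9.6.2 does not label the curve as cause-specific, and readers commonly take such a curve as absolute risk.
- **Details are left to the SAP, and censoring at death is inferred.** Both are true, which is why the point is limited to the text as written. The protocol does fix the estimator, the event and the censoring rule, so a SAP that follows it inherits the bias.
- **The size rests on assumptions.** This stands. The case mix is assumed, f = 1 is an upper bound, and a transfusion-independent population with few blasts may have lower hazards than the Appendix C cohort. If the sponsor ends the trial early through a roll-over protocol (section 3.3), follow-up will be shorter and the gap smaller.
- **With about 20 subjects and about 3 AML events, noise dominates.** This also stands for the average bias. The exact 95% interval for 3/20 runs from 3% to 38%. However, an interval displays sampling error, whereas this bias is systematic and hidden. The disagreement also arises within the same subjects, so sampling error does not explain it.

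**Conclusion.** The concern holds for the plan as written. The direction is certain: if AML-free deaths are censored and any of them precedes an AML event, one minus Kaplan-Meier exceeds the probability of AML. For a mixed cohort at 5 years the excess is roughly 2 to 6 points under constant Appendix C hazards and the assumed mixes. It is larger for Intermediate-risk subjects alone, about 0.5 to 1 point if both risks are low, and negligible at 1 year. The consequence is confined to one descriptive curve, chiefly at the final follow-up analysis. The sponsor should correct it, but it does not threaten the trial's conclusions.

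**What to change.** Amend section 9.6.2, and carry into the SAP, wording to this effect: death without AML is a competing event and not a censoring event; progression to AML is estimated by the Aalen-Johansen cumulative incidence function with 95% confidence intervals at 1, 3 and 5 years; subjects alive without AML are censored at their last assessment.

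Keep the count and percentage progressing to AML. Use Kaplan-Meier only for a composite of AML or death, if one is wanted. If the sponsor prefers to keep the present curve, the minimum is to label it as cause-specific and direct readers to the percentage for absolute risk.

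The cost is one sentence in each document and one standard procedure. No new data are needed, because section 6.3.2 already collects date and cause of death. The drawback is wide intervals with so few events, which the present method shares.

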9.7. Safety Analysis

All safety analyses will be performed on the safety population. Full details will be included in the SAP. Planned data presentations and analyses include the following:

Adverse events will be coded using MedDRA. Adverse event listings will include the verbatim term and the MedDRA preferred term. Treatment-emergent adverse events will be summarized by system organ class and preferred term. Treatment-emergent adverse events leading to death or to discontinuation from treatment, treatment-emergent adverse events (TEAEs) classified as National Cancer Institute (NCI) Common Terminology Criteria for Adverse Events (CTCAE) (version 4.03) all grades or grade 3/4 TEAEs, related to investigational product, and serious TEAEs will be summarized separately.

Clinical laboratory results will be summarized descriptively. Clinically significant hematologic and non-hematologic laboratory abnormalities will be listed and summarized according to the NCI CTCAE (version 4.03). Additionally, frequency of ADAs will also be reported.

Physical examination data and vital sign measurements, including body weight, will be listed for each subject at each visit. Descriptive statistics for vital signs, both observed values and changes from baseline, will be summarized.

